Transplanted patients will be followed through an echocardiographic evaluation (enrolment and 3-6-12 months follow-up), to evaluate cardiac functional parameters, metabolic parameters and survival outcomes (death for all causes, cardiac death, re-hospitalisation for heart failure). In all transplanted patients endo-myocardial biopsies (EMB) are collected according to normal clinical practice by the "ASHI" guideline (9): weekly for the first month; every 2 weeks for the following month; 1 for the following 4 weeks; 1 for the following 6 weeks; every 3 months for the following 2 years; and finally every 6 months for the following 3 years. 2-6 (usually 4, 1 to 3 mm³) fragments of myocardial tissue will be collected from the apical segment of the right side of the interventricular septum (IVS). The collected myocardial tissue will be immediately analyzed for histopathological evaluation of rejection. From the remaining portion of tissue 3 portions will be obtained: one portion will be incorporated into the OCT compound for immunohistochemical analysis, a second portion will be frozen immediately in liquid nitrogen and stored at -70°C for PCR evaluation, and a third portion will be used for quantitative evaluations performed by ELISA. The conservation and morpho-functional evaluation of biopsy samples will be carried out at the Bio-Bank of the University of Campania "Luigi Vanvitelli".

Biopsies analysis

PCR.

Total RNA will be isolated from human heart sample homogenates using the RNeasy Mini kit (74106, Qiagen), according to the manufacturer's protocols "Stabilization of RNA in collected animal tissues" and "Purification of total RNA from animal tissues". RNA concentration and purity will be determined using the NanoDrop 2000c (Thermo Fisher Scientific) spectrophotometer. Genomic DNA (gDNA) contamination will be removed from RNA samples prior to the Reverse Transcription (RT) phase, performed on the Gene AMP PCR System 9700 (Applied Biosystems)

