Study population groups (diabetics vs. non-diabetics) will be compared using the Pearson test for categorical variables and the Kruskal-Wallis test for continuous variables. Candidates for admission to the multivariate model will be identified by focusing on factors that will differ significantly (P value < 0.05) in the univariate analysis among diabetic vs non-diabetic patients. Cox regression will be used to construct the predictive model of mortality. The risk ratio for mortality will be adjusted by age, BMI, cholesterol, LDL, triglycerides and aspirin, ticlopidine, anti-aggregants, beta-blockers, ACE inhibitors or tailors, antidiabetic drugs, statins, etc. present at the time of admission to hospital for cardiac transplantation. The analysis of survival after cardiac transplantation will be performed using the Kaplan-Meier curve and the Cox regression method. Mortality curves will be obtained separately for diabetic and non-diabetic patients, and then compared using the log-rank test. All tests will be considered significant if they have a value of $p < 0.05$. All tests will be conducted in 2 populations: diabetic vs non-diabetic patients after cardiac transplantation. The SPSS program (version 21, IBM SPSS) will be used for all analyses.

References

2. L López-Sainz Á, Barge-Caballero E, Barge-Caballero G, Couto-Mallón D, Paniagua-Martin MJ, Seoane-Quiroga L, Iglesias-Gil C, Herrera-Noreña JM, Cuenca-Castillo JJ, Vázquez-Rodríguez JM, Crespo-Leiro MG. Late graft failure in heart transplant recipients: incidence, risk factors and clinical outcomes. *Eur J Heart Fail.* 2018;20:385-394.

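### Candidates for the mortality model are screened on whether they differ by diabetes status, not on whether they are expected to predict death; how this screen fits with the named adjustment list, and when screened factors are measured, is not stated

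*Combined protocol and SAP*

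**What the plan says.** All of the model text is in the Statistical analysis section of the combined protocol and SAP.

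- **Group comparison.** Diabetic and non-diabetic patients "will be compared using the Pearson test for categorical variables and the Kruskal-Wallis test for continuous variables".
- **Screen.** "Candidates for admission to the multivariate model will be identified by focusing on factors that will differ significantly", with the criterion given as "P value < 0.05) in the univariate analysis among diabetic vs non-diabetic patients".
- **Model.** "Cox regression will be used to construct the predictive model of mortality".
- **Named adjustment list.** "The risk ratio for mortality will be adjusted by age, BMI, cholesterol, LDL, triglycerides and aspirin", followed by other drug classes and an open-ended et cetera. These are the values "present at the time of admission to hospital for cardiac transplantation".
- **Population.** "All tests will be conducted in 2 populations: diabetic vs non-diabetic patients after cardiac transplantation".

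Separately, the section on endomyocardial biopsies and follow-up schedules "echocardiographic evaluation (enrolment and 3-6-12 months follow-up), to evaluate cardiac functional parameters, metabolic parameters and survival outcomes", together with serial biopsies.

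No sample size, expected number of deaths or effect size is given anywhere.

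**The concern.** The screen and the model have different targets. The screen asks whether a factor differs between diabetic and non-diabetic patients; the model is meant to predict death. Association with death, or prior knowledge of prognosis, is nowhere an entry criterion.

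The rule serves neither of the purposes the model could have. For prediction, it discards strong predictors that happen to be balanced and admits factors that differ by diabetes but have no bearing on death. For an adjusted diabetes effect, it makes control of a confounder depend on whether a significance test in a cohort of unstated size happens to detect the imbalance.

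Two gaps in wording add to this. The plan does not say whether the named list is forced into the model or is itself subject to the screen. And the admission-time restriction is attached to the list, not to the screening sentence, so the eligibility of values measured after transplantation is left open.

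**Working it through.** The plan states no figure on this point, so there is none to reproduce. The threshold of 0.05 is from the Statistical analysis section. Tests are taken as two-sided (sidedness is not stated), and group sizes, imbalances and hazard ratios are assumed.

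**1. Prognostic factor balanced between groups.** The null hypothesis of the screen is true, so the factor passes with probability 0.05 at any sample size and any strength of association with death. A simulated Kruskal-Wallis screen (1000 runs, factor with hazard ratio 2 per SD) gave 4.7% at 50 per group and 5.4% at 100.

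**2. Binary confounder, 30% v 50%.** Pooled proportion 0.40.

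Power = Φ{[0.20 − 1.96·√(2·0.40·0.60/n)] / √[(0.30·0.70 + 0.50·0.50)/n]}

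- n = 25 per group: (0.20 − 1.96·0.1386)/0.1356 = −0.528, so power 0.299; missed 70%.
- n = 50 per group: (0.20 − 1.96·0.0980)/0.0959 = 0.083, so power 0.533; missed 47%.

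**3. Continuous factor, difference d in SD units.** Probability of passing ≈ Φ(d/√(2/n) − 1.96).

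| n per group | d = 0.3 | d = 0.8 |
|---|---|---|
| 25 | 18% | 81% |
| 50 | 32% | 98% |
| 100 | 56% | about 100% |

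The calculation does not involve the factor's relation to death. A factor unrelated to death that differs by 0.8 SD is therefore admitted far more readily than a true confounder that differs by 0.3 SD.

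**4. Effect on the diabetes hazard ratio.** Simulation with a true diabetes hazard ratio of 2.0, one prognostic factor (hazard ratio 2 per SD), one non-prognostic factor shifted by 0.8 SD, and censoring at 12 months; 1000 runs per row.

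| n per group | Shift of prognostic factor | Median HR, screened | Median HR, factor pre-specified |
|---|---|---|---|
| 50 | 0 | 1.93 | 2.02 |
| 50 | 0.3 SD | 2.10 | 2.02 |
| 100 | 0 | 1.94 | 2.02 |
| 100 | 0.3 SD | 2.06 | 2.00 |

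**5. Timing, from the text.** The only measurement time given for any model covariate is admission for transplantation, and it belongs to the named list. The screening sentence has none. The follow-up section lists measurements at 3, 6 and 12 months but does not connect them with the Cox model.

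**The case against.** **The named list protects the main covariates.** The sentence on adjustment reads most naturally as a fixed set, so age, BMI, lipids and the listed drugs would stay whatever the screen finds. This stands, and the point is limited to factors outside that list. It does not remove the point: the list names no cardiac function, renal or donor variable, so such factors can enter only through the screen or the et cetera. If the list were the whole model, the screening sentence would have no purpose.

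**The bias in the diabetes effect may be small.** A balanced factor is not a confounder, and in the simulation the screen moved the hazard ratio only to between 1.93 and 2.10 against a true 2.0. This also stands for the single-factor case assumed. It does not help the predictive aim, for which dropping prognostic factors is the failure itself.

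**The screen only nominates candidates.** Final selection is not described. That is true, but a factor that is not nominated has no stated route in other than the list.

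**A stronger reading that does not hold.** A reader might infer that echo, metabolic or biopsy values from months 3 to 12 will be entered as fixed covariates, so that early deaths are lost and consequences of diabetes are adjusted away. The documents do not say this. The phrase about patients after transplantation, in "All tests will be conducted in 2 populations: diabetic vs non-diabetic patients after cardiac transplantation", names the population; it does not say when the factors are measured. What remains is that the wording does not rule such entry out.

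**Conclusion.** The concern holds in limited form. The stated rule selects on association with diabetes and is unsuited to a model meant to predict mortality. Followed literally, for factors outside the named list it drops about 95% of balanced prognostic factors and, at an assumed 25 or 50 per group, misses a 30% v 50% confounder 70% or 47% of the time. The 95% follows from the threshold alone. The other figures depend on assumed group sizes and imbalances and would shrink in a larger cohort or with a larger imbalance.

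The relation between screen and list is undefined, and post-transplant values are not excluded. Both are gaps in wording. No size can be put on the second, because the plan does not propose to use such values in the model.

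The stated aim of the study is cellular change in the explanted and transplanted heart, and the mortality model is one of several analyses. The change should be made, but the point does not call the whole study into question.

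**What to change.** In the Statistical analysis section:

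1. Delete the P < 0.05 group-difference screen as a route into the model. The group comparisons can stay as description.
2. Fix the covariate set before outcome data are seen: the named list, with the et cetera replaced by explicit items, plus any further factors chosen because they are expected to predict death or to confound the diabetes comparison. State that the whole set is included regardless of group differences.
3. Limit the set to variables measured at or before transplantation.
4. State that if a later echo, metabolic or biopsy value is used, it enters only as a time-dependent covariate, or in a landmark analysis that starts at its measurement date.

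The cost is a few sentences and no new data. The downside is that the investigators must agree the covariates in advance instead of reading them off the comparison table.

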Unique Protocol ID: DCM-AHEAD

**Brief Title: Diabetes and Lipid Accumulationand Heart Transplant
(DCM-AHEAD)**

Official Title: Lipid Accumulation in Heart Transplant From Non-diabetic Donors to Diabetic Recipients

Project manager: [name]

Department of Advanced Medical and Surgical Sciences

[contact]

e-mail: [contact]

clinical trial number: NCT03546062

clinical trial registry: clinicaltrialgov.com

Naples November 19, 2019

BACKGROUND

[figure not shown]
Idiopathic dilated cardiomyopathy (IDC) is defined by the presence of left ventricular systolic dysfunction in the absence of an abnormal loading condition or significant coronary heart disease (1). IDC is the leading cause of end-stage heart failure (HF) and is responsible for half of all heart transplants (HTx) (1). Endocrine disorders, including diabetes, are known to be associated with IDCs. Diabetes mellitus (DM), which is present in 75% of patients with idiopathic IDC, is an independent risk factor for the development of heart failure and death in IDC (2-4). Therefore, DM may exacerbate the need for HTx; moreover, diabetic patients are less suitable for HTx and DM remains an independent risk factor for death even after HTx (5). Recent studies have revealed the presence of diabetic cardiomyopathy, a condition of myocardial dysfunction without coronary heart disease (6, 7). This term was first introduced by Rubler et al. (8) in 1972, which highlighted patients with diabetes and congestive heart failure with normal coronary arteries. The pathophysiological mechanisms by which diabetes affects the development and progression of diabetic heart disease are not known. Therefore, the aim of our study will be to evaluate, in the diabetic heart removed, the presence of any cellular alterations related to diabetic disease. In addition, the progression of such lesions in the transplanted heart in diabetic patients will be evaluated.

MATERIALS AND METHODS

Study protocol

A prospective observational study will be conducted with a follow-up duration ranging from a minimum of 12 months to a maximum of 36 months (Figure).

STUDY PROTOCOL

Patients

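### The mortality Cox model has two unreconciled covariate rules, and both point to antidiabetic drugs, which can leave the diabetes hazard ratio resting on untreated diabetics

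*Combined protocol and SAP*

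**What the plan says.** All the modelling text is in the Statistical analysis section.

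- **Screen.** Groups are "compared using the Pearson test for categorical variables and the Kruskal-Wallis test for continuous variables". Candidates for the multivariate model are "factors that will differ significantly (P value < 0.05) in the univariate analysis among diabetic vs non-diabetic patients". The screen looks at the difference between exposure groups, not at any relation to death, and no step is given for moving from candidate to model term.
- **Named list.** "The risk ratio for mortality will be adjusted by age, BMI, cholesterol, LDL, triglycerides and aspirin, ticlopidine, anti-aggregants", and the sentence runs on through further drug classes to "antidiabetic drugs, statins, etc. present at the time of admission to hospital for cardiac transplantation". That is twelve named items plus an open ending. Antidiabetic drugs are one of the twelve; their coding is not stated.
- **Model.** "Cox regression will be used to construct the predictive model of mortality". Diabetes is not named as a term. The diabetic versus non-diabetic mortality contrast is explicit for the Kaplan-Meier curves and log-rank test.

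Mortality is one of the "survival outcomes (death for all causes, cardiac death, re-hospitalisation for heart failure" in the follow-up section. The Background states a tissue aim: "the aim of our study will be to evaluate, in the diabetic heart removed, the presence of any cellular alterations related to diabetic disease".

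**The concern.** Two analysts could both follow this section faithfully and fit different models, because it does not say whether the screen filters the list, adds to it, or is replaced by it.

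Choosing one rule over the other would not settle the matter. Use of antidiabetic drugs is close to a proxy for having diabetes. The list names it, and the screen favours whatever separates diabetics from non-diabetics most sharply. Once such a term sits beside diabetes, the diabetes coefficient no longer describes diabetics as a whole. At stake are what the adjusted HR means, how precise it is, and in a small cohort whether it can be estimated at all.

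**Working it through.** The documents give no sample size, number of deaths, power or treated share, so there is no figure of the plan's own to reproduce. Taken from the documents: the Pearson test, the 0.05 level, the named list and the two-group contrast. Everything else below is assumed and marked so.

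**1. Would the drugs pass the screen?** Assume n per group, k treated diabetics and no treated non-diabetics. The Pearson statistic without continuity correction reduces to 2nk/(2n − k).

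- k = 21, n = 30: 60 × 21/39 = 32.3, P = 1.3 × 10⁻⁸.
- k = 4, n = 30: 60 × 4/56 = 4.29, P = 0.038. With k = 3 it is 60 × 3/57 = 3.16, below the critical value of 3.84.
- At k = 4 the statistic exceeds 4 for every n, so four treated diabetics suffice at any size from 10 to 100 per group (P = 0.025 to 0.043).
- If only 30% of diabetics are treated, the chance of at least four is 0.893, 0.991 and 0.999 at 20, 30 and 40 per group.

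**2. What does the diabetes coefficient then mean?** Let the log hazard be b_D·D + b_T·T, with D diabetes and T any antidiabetic drug (yes/no), and T = 0 for every non-diabetic. Relative to non-diabetics, untreated diabetics have b_D and treated diabetics have b_D + b_T. As b_T is free, treated diabetics inform b_T and not b_D.

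- Simulation check (100 per group, 80% treated, true diabetes HR 2): the model with both terms gave HR 2.00, SE 0.31. Deleting every treated diabetic gave HR 1.99, SE 0.31. The two estimates correlated at 0.996.
- If all diabetics are treated, D and T are the same column and b_D cannot be estimated.
- If the drugs do affect death, the target moves too. With an assumed drug HR of 0.6, a rough average over diabetics is 0.8 × (2 × 0.6) + 0.2 × 2 = 1.36. Simulation gave 1.39 without the drug term and 2.09 with it.
- With two drug-class terms and no untreated diabetics, the model has full rank and b_D is estimated (HR 2.10, SE 0.12 at 1000 per group), but only by assuming that class effects add and extrapolating to no drug.

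**3. How much precision is lost?** Cox simulation, 1000 runs per setting. Assumed: half the cohort diabetic, 15% deaths, diabetes HR 1.5, age and BMI shifted by 0.4 SD, and no drug effect on death. In the screen rows every factor that passed was entered. Median SE of the diabetes log HR:

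| N, rule | Without antidiabetic drugs | With them, 70/80/90% treated | Ratio |
|---|---|---|---|
| 100, list | 0.67 | 0.92 / 1.03 / 1.22 | 1.37 / 1.54 / 1.82 |
| 100, screen | 0.60 | 0.82 / 0.89 / 1.10 | 1.37 / 1.48 / 1.83 |
| 200, list | 0.43 | 0.58 / 0.65 / 0.83 | 1.35 / 1.51 / 1.93 |
| 200, screen | 0.42 | 0.56 / 0.63 / 0.80 | 1.33 / 1.50 / 1.90 |

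At N = 100 with the list and 80% treated, the 95% limits lie a factor exp(1.96 × 1.03) = 7.5 either side of the HR, against exp(1.96 × 0.67) = 3.7 without the drugs. No usable HR (no convergence, or absolute log HR above 6) arose in 4%, 13% and 38% of runs at N = 100, against at most 0.2% without the drug term. At N = 200 it was 0.1%, 1.5% and 11%.

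**4. Cross-check by formula.** With treated share p and diabetic share q = 0.5, the variance inflation is (1 − pq)/(1 − p): 0.65/0.3 = 2.17, 0.6/0.2 = 3.0 and 0.55/0.1 = 5.5. The square roots are 1.47, 1.73 and 2.35. This corresponds to equal deaths in the two groups and no other covariates, so it is an upper guide here; more deaths among diabetics lower it. If 5% of non-diabetics also take the drugs, the square roots are 1.35, 1.53 and 1.90.

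**The case against.** The strongest reply is that the adjusted diabetes HR is itself an inference. The section speaks of a predictive model and a mortality risk ratio without naming an exposure. For pure prediction, an unstable diabetes coefficient is not in itself a fault. The sentence placing all tests in two populations could even be read as modelling within each group, where adjusting for antidiabetic drugs among diabetics is ordinary. This stands as a limit. A diabetes HR remains the natural reading, because the whole section is framed as diabetic versus non-diabetic.

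Three stronger readings are tempting and should not be drawn.

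- *The drugs are bound to enter under either rule.* That follows from the list. The screen yields only candidates, and with no entry step stated, a later selection on mortality could drop them.
- *The HR as written rests on untreated diabetics only.* This needs diabetes as a model term, one yes/no drug variable and no non-diabetic users. The documents state none of the three.
- *The SE rises 1.5, 1.7 or 2.3 times.* Those are the formula values; the simulated increases are smaller.

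It is also fair that the unadjusted survival comparison is untouched and that mortality sits beside a tissue aim.

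**Conclusion.** The concern holds in conditional form. The two covariate rules and the missing link between them are plain in the text, as is the presence of antidiabetic drugs on the list. That the drugs would become candidates under the screen is close to certain for any realistic treated share.

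The consequence depends on the three coding conditions given under the objection. If they hold, only untreated diabetics identify the diabetes HR, and with none it is not estimable. The SE increase of about 1.4, 1.5 and 1.8 to 1.9 times at 70%, 80% and 90% treated also rests on an assumed cohort size, death rate and group split. With separate drug-class terms the loss takes another form: treated diabetics count only through extrapolation.

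This should be corrected before analysis, because it changes what the adjusted HR estimates as well as how precisely. It does not threaten the Kaplan-Meier and log-rank comparison or the tissue analyses.

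**What to change.** In the Statistical analysis section:

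1. Name diabetes as the exposure in the mortality Cox model.
2. For that model, delete the sentence that screens candidates at P < 0.05, and delete the etc.
3. Adjust for one fixed list drawn from the items the section already names, leaving out antidiabetic drugs. Any drug effect can be analysed among diabetics only, with the coding stated.
4. Report the unadjusted diabetes HR beside the adjusted one.
5. If a separate predictive model of mortality is kept, give its covariates separately and label it exploratory.

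The cost is SAP wording only, since the items are already planned as admission data. The downside is that fewer covariate effects are reported in the main model. Under the assumptions above, with the named list and 80% treated, dropping the drug term takes the SE from 1.03 to 0.67 at N = 100 and from 0.65 to 0.43 at N = 200.

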using the QuantiTect Reverse Transcription Kit (205311, Qiagen), according to the "Reverse Transcription with Elimination of Genomic DNA for Quantitative, Real-Time PCR" protocol. The final step for real-time PCR analysis (qPCR) will be performed on the CFX96 Real-time System C1000 Touch Thermal Cycler (BIORAD). The analysis will be performed according to the "Two-Step RT-PCR (Standard Protocol)" protocol, using the QuantiTect SYBR Green PCR Kit (204143, Qiagen) and specific QuantiTect Primer Assays (249900, Qiagen) for each gene tested. Relative quantization of gene expression will be performed using the $2^{-\Delta\Delta Ct}$ method, using GAPDH as the cleaning control gene. P values will be calculated on the basis of a student t-test or one-way variance analysis (ANOVA), followed by Dunnett's post hoc test; $P < 0.05$ will be considered significant.

Immunofluorescence. Confocal laser scanning microscopy.

The analysis of immunofluorescence in sections of the myocardium will be performed according to the manufacturing protocol using the laser scanning confocal microscope (LSM 700; Zeiss). In particular, the complete removal of the paraffin will be carried out before proceeding to the staining of the section. For this purpose, the slides will be deparaffinized by passing them through xylenes, alcohols and water. An antigen recovery buffer (10 mM sodium citrate, 0.05% Tween 20, pH 6.0) will be added to the dewaxed and rehydrated sections and boiled in the microwave for 20 minutes. After 20 minutes, immunofluorescence staining will be performed using specific antibodies against PPAR-alpha (1 μ g/ml) (polyclonal rabbit, NB600-636, Novusbio, Abingdon, UK), PPAR-gamma (1 μ g/ml) (mouse monoclonal, orb69095, Biorbyt, Cambridge, UK) or against SREBP1 (1 μ g/ml) (polyclonal rabbit, ab28481, Abcam, Cambridge, UK). Secondary antibodies will be conjugated with Alexa Fluor 633 or Alexa Fluor 488 (Life Technologies Italia, Monza, Italy). Nuclear contrast staining will be performed using the VECTASHIELD® mounting medium with DAPI (H-1200, Vector Laboratories, Burlingame, USA).

Immunohistochemistry.

Oil Red O (Solvent Red 27, Sudan Red 5B, C.I. 26125, C26H24N4O) will be used for the assessment of the accumulation of intramyocytic lipids.

Statistical analysis

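### The only adjusted mortality ratio conditions on blood lipids and diabetes treatment recorded at transplant admission, so it may not be the total effect of diabetes, and the plan does not say which effect it means

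*Combined protocol and SAP*

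**What the plan says.** The Statistical analysis section sets the contrast: "Study population groups (diabetics vs. non-diabetics) will be compared". For death it says "Cox regression will be used to construct the predictive model of mortality", and then "The risk ratio for mortality will be adjusted by age, BMI, cholesterol, LDL, triglycerides". The same sentence goes on to antiplatelet drugs, beta-blockers and other cardiac drugs, and ends with "antidiabetic drugs, statins, etc. present at the time of admission to hospital for cardiac transplantation". I read the admission time point as applying to the whole list.

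A separate rule in that section makes a factor a candidate for the multivariable model if it differs between diabetic and non-diabetic patients at P < 0.05. Survival is also shown by Kaplan-Meier curves for the two groups, compared by a log-rank test.

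The section states no estimand, gives no reason for the covariate list, and specifies no second adjustment set. Sex is not among the named covariates.

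**The concern.** Diabetes is already present or absent when the admission lipids and drugs are recorded, so those variables can be affected by it. A covariate on the path from exposure to outcome is not a confounder of the total effect. Conditioning on it changes the question to how much diabetes matters among patients with the same lipids and the same treatment.

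That is a legitimate question, but the plan does not say it is the one being asked. A reader would naturally take the single adjusted ratio as the answer to whether diabetes affects survival after transplantation. If it came out near 1, it could be reported as no effect of diabetes when the model had answered something narrower.

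Two features of the plan add to this. Antidiabetic drugs are tied more closely to the exposure than the lipids are. And a rule that admits covariates because they differ by diabetes status favours variables linked to diabetes, whether they precede it or follow from it.

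**Working it through.** **1. What each planned mortality analysis estimates**

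| Analysis | Adjusted for age | Conditions on lipids and antidiabetic drugs |
|---|---|---|
| Kaplan-Meier and log-rank | no | no |
| Cox model with the stated list | yes | yes |
| Cox model with factors not plausibly caused by diabetes | not planned | not planned |

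The third row is the one that would give a confounder-adjusted total effect.

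**2. Antidiabetic drugs**

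Assume the covariate is a yes/no indicator and no non-diabetic recipient takes such a drug. With diabetes and this indicator both in the model, the diabetes coefficient compares diabetics *not* on drug treatment with non-diabetics. The difference for treated diabetics is split between two coefficients. This follows from the coding alone, whatever the mechanism.

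**3. Size of the lipid effect**

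The documents give no number of patients, number of deaths, mortality rate or effect size, so there is no figure to reproduce. Everything below is assumed. Let *a* be the shift in a lipid variable between diabetics and non-diabetics, in standard deviations, and *b* the log hazard ratio of death per standard deviation. With the lipid on the path, approximately

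log HR(adjusted) = log HR(total) − *a* × *b*

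| *a* | *b* | *a* × *b* | Total HR 2.0 becomes | Total HR 1.5 becomes |
|---|---|---|---|---|
| 0.2 | 0.1 | 0.02 | 1.96 (3% of log HR removed) | 1.47 (5%) |
| 0.5 | 0.3 | 0.15 | 1.72 (22%) | 1.29 (37%) |
| 0.8 | 0.3 | 0.24 | 1.57 (35%) | 1.18 (59%) |
| 0 | 0.3 | 0 | 2.00 (0%) | 1.50 (0%) |
| −0.3 | 0.3 | −0.09 | 2.19 (13% added) | 1.64 (22% added) |

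Example: exp(ln 2.0 − 0.5 × 0.3) = exp(0.693 − 0.150) = 1.72, and 0.150 / 0.693 = 22%. The last row is the case where diabetics have *lower* lipids, for example through statins.

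**4. Check by simulated Cox models**

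Each setting used 8 runs of 20,000 simulated patients and an assumed baseline hazard of 0.1 over one unit of follow-up.

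| Assumed structure | HR without lipid | HR with lipid | Ratio |
|---|---|---|---|
| Lipid on the path, *a* = 0.5, *b* = 0.3, total HR 2.0 | 2.05 | 1.78 | 0.87 |
| Lower lipid in diabetics, *a* = −0.3, *b* = 0.3, total HR 2.0 | 2.02 | 2.23 | 1.10 |
| Lipid shares a cause with diabetes, no mediation, true HR 2.0 | 2.17 | 1.96 | 0.90 |

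The levels carry simulation error of a few per cent (1.78 against 1.72 by formula). The ratio within a row is steadier: 0.87 against exp(−0.15) = 0.86, and 1.10 against exp(0.09) = 1.09.

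In the first two rows the model *without* lipid estimates the total effect. In the third row the model *with* lipid is closer to the truth. Rows one and three both show the ratio falling when lipid is added, so observing a fall would not show which structure applies.

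**The case against.** A reader might infer something stronger: that the study is about diabetes harming the heart through lipid, that blood lipids are consequences of diabetes, and that adjusting for them therefore biases the ratio toward no effect. The documents do not support that reading.

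- The title is "Lipid Accumulation in Heart Transplant From Non-diabetic Donors to Diabetic Recipients", but the Background says "The pathophysiological mechanisms by which diabetes affects the development and progression of diabetic heart disease are not known". Lipid accumulation is what will be observed, not a declared route to death.
- The lipid under study is in the myocyte: Oil Red O "will be used for the assessment of the accumulation of intramyocytic lipids". That measure is not in the adjustment list. Conditioning on a blood lipid at admission does not adjust away lipid that later accumulates in the graft, and the documents do not say how closely the two are linked.
- Nothing in the documents says that cholesterol, LDL or triglycerides follow from diabetes. They could precede it, share causes with it, or be lowered by statins. Section 4 of the working shows all three directions of change are possible in principle.

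Those points stand, and they rule out any claim about direction or size.

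Three further defences carry less weight. The model is called predictive, and lipids are proper predictors; but the plan also speaks of an adjusted ratio and frames its comparisons as diabetic versus non-diabetic. That the ratio is the one for diabetes is an inference, though the natural one. The log-rank test does not condition on lipids; but it is not adjusted for age or anything else, so it cannot stand in for a confounder-adjusted estimate. Finally, the stated aim is "to evaluate, in the diabetic heart removed, the presence of any cellular alterations related to diabetic disease" and the progression of such lesions in the graft, with death only a follow-up outcome. That limits the importance of the point without removing it.

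**Conclusion.** The point holds in a limited form. Following the plan gives no confounder-adjusted estimate of the total effect of diabetes on death. The one adjusted ratio conditions on variables that may lie on the path, and the plan does not say which effect it is meant to estimate.

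The size is unknown. The ranges in the working (1.57 to 2.19 for a total hazard ratio of 2.0, and 1.18 to 1.64 for 1.5) rest wholly on assumed *a*, *b* and hazard ratios, and show only that the choice of list can matter or can be immaterial. A statement that the planned ratio is biased toward the null, or understates diabetes by some percentage, would go beyond the documents.

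This is a low-cost improvement, not a threat to the study's main aim. It does change what may be concluded about diabetes and death.

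**What to change.** 1. State that the diabetic versus non-diabetic mortality ratio is intended as the total effect of diabetes. If only prediction is meant, say so and do not present the ratio as an effect of diabetes.
2. Beside the planned model, report a Cox model adjusted only for factors not plausibly caused by diabetes, such as age, sex and entry severity, as the number of deaths allows, without blood lipids or antidiabetic drugs. Fix this list in advance, outside the P < 0.05 rule, with a reason for each entry. Entry severity and BMI need that reason most: the Background links diabetes to the development of heart failure, and BMI may precede diabetes or change with it.
3. Label the planned model as additionally adjusted for lipids and treatment. Note that reading it as the effect not passing through lipids requires no unmeasured confounding between lipids and death. Because the two models also differ in drugs, the gap between them should not be credited to lipids alone.
4. Do not read a null from the planned model alone as no effect of diabetes.

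Cost: one more model and a label, with little or no extra data. The downside is that lipid differences that pre-date diabetes stay unadjusted in the smaller model, which is why both should be shown.
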